By design, patients in the HCR group will undergo planned staged procedures, and patients in the PCI group may or may not undergo planned staged procedures. The treatment strategy for staged procedure will be collected at the time of the first index procedure. Regardless of treatment assignment (HCR or PCI group), the revascularization strategy for staged procedures must be completed (in all cases) within *90 days* after the first revascularization intervention after randomization, with ≤ 60 days recommended. Unplanned ischemia-driven procedures at any time, and all procedures performed >90 days after the first post-randomization revascularization intervention will be considered endpoint events.

To minimize ascertainment bias in the identification of peri-procedural MI, baseline cardiac biomarkers (CK-MB and/or Troponin T or I) and an electrocardiogram (ECG) must be performed in all patients prior to CABG and PCI. For patients with stable CAD, the baseline biomarkers may be sent at the time of the first procedure, before revascularization. An ECG must be repeated once within 24 hours after each revascularization procedure, and the biomarkers must be repeated at least twice within 24 hours after each procedure (at 12 ± 4 hours and at 24 ± 4 hours, or at discharge if sooner than 24 hours).

Hybrid Coronary Revascularization

HCR is defined, for the purposes of this trial, as a planned off-pump, minimally invasive (sternal-sparing) isolated LIMA-LAD revascularization, combined with percutaneous revascularization of at least one non-LAD target. The revascularization targets and procedural timing strategy to be utilized should be outlined prior to the initial revascularization procedure. Three possible timing strategies may be used: surgery followed by PCI on separate calendar days, PCI followed by surgery on separate calendar days, or concomitant (simultaneous) PCI and surgery (defined as: a. PCI followed by CAGB in the same room on the same day, or b. CABG followed by PCI in the same room on the same day, or c. PCI followed by CABG in different rooms on the same day, or d. CABG followed by PCI in different rooms on the same day). The specific strategy adopted will be collected and categorized. The complete revascularization strategy, if staged, must be completed within *90 days* of the first revascularization intervention (≤ 60 days preferred).

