Stroke (ischemic or hemorrhagic) is defined as the rapid onset of a new neurological deficit attributed to an obstruction in cerebral blood flow and/or cerebral hemorrhage with no apparent non-vascular cause (e.g., trauma, tumor, or infection) that i) persists beyond 24 hours, or ii) less than 24 hours if: a) associated with infarction or hemorrhage on an imaging study, or b) treated with pharmacologic or mechanical intervention, or c) results in death. Patients with non-focal global encephalopathy will not be reported as a stroke without unequivocal evidence based upon neuroimaging studies. In most cases a vascular neurologist or stroke specialist will determine whether a stroke has occurred. Available neuroimaging studies will be considered to support the clinical impression and to determine if there is a demonstrable lesion compatible with an acute stroke. Strokes will be classified as ischemic, hemorrhagic, or unknown. Hemorrhagic conversion of an ischemic stroke should be classified as ischemic.
- *Myocardial Infarction*

A. Non-Procedure Related Myocardial Infarction³

The Third Universal Definition of Myocardial Infarction will be used to define Non-Procedure Related Myocardial Infarction. This definition applies to an event occurring >48 hours after any revascularization procedure as follows:

Detection of rise and/or fall of cardiac biomarkers (preferably troponin) with at least one value above the 99th percentile of the upper reference limit (URL) of the assay together with evidence of myocardial ischemia with at least one of the following:

- Symptoms of ischemia;
- ECG changes indicative of new ischemia (new ST-T changes or

- new left bundle branch block [LBBB]);
- Development of pathological Q waves in the ECG;
- Imaging evidence of new loss of viable myocardium or new regional wall motion abnormality.

In the absence of knowledge of the URL, the local laboratory upper limit of normal (ULN) may be substituted.

Note: Sudden unexpected cardiac death, involving cardiac arrest, often with symptoms suggestive of myocardial ischemia, and accompanied by presumed new ST elevation or new LBBB, and/or evidence of fresh thrombus by coronary angiography and/or autopsy, with death occurring before blood samples obtained, or at a time before the expected appearance of cardiac biomarkers in blood will be classified as a mortality due to spontaneous MI.

B. Peri-PCI and Peri-CABG Myocardial Infarction⁴

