The SCA&I definition of a clinically relevant peri-procedural myocardial infarction (MI) will be used for this definition. CK-MB is the preferred biomarker for post revascularization assessment of myonecrosis, but cardiac troponin I or T may be used as described below. A baseline pre-procedure value should be measured in all patients, and 2 additional biomarker measurements must be measured post procedure at 12 ± 4 hours and 24 ± 4 hours post- procedure. If any measurement is elevated, serial measures should be repeated until the peak is reached and the levels are returning toward baseline. This definition applies to an event occurring ≤ 48 hours after any revascularization procedure as follows:

- a. In patients with normal baseline CK-MB: The peak CK-MB measured within 48 hours of the procedure rises to ≥ 10 times the local laboratory ULN, or to ≥ 5 times ULN with new pathologic Q-waves in ≥ 2 contiguous leads or new persistent LBBB, OR in the absence of CK-MB measurements and a normal baseline cTn, a cardiac troponin (cTn) I or T level measured within 48 hours of the PCI rises to ≥ 70 times the local laboratory ULN, or ≥ 35 times ULN with new pathologic Q-waves in ≥ 2 contiguous leads or new persistent LBBB. If baseline CK-MB or cTn is unavailable in a patient with stable CAD, they will be assumed to be normal.
- b. In patients with elevated baseline CK-MB (or cTn) in whom the biomarker levels are stable or falling: The CK-MB (or cTn) rises by an absolute
- c. increment equal to those levels recommended above from the most recent pre- procedure level.
- d. In patients with elevated CK-MB (or cTn) in whom the biomarker levels have not been shown to be stable or falling, or in the patients with ACS without a baseline CK-MB or cTn measure: The CK-MB (or cTn) rises by an absolute increment equal to those levels recommended above *plus* new ST-segment elevation or depression *plus* signs consistent with a clinically relevant MI, such as new onset or worsening heart failure or sustained hypotension.

³Joint ESC/ACCF/AHA/WHF Task for the Redefinition of Myocardial Infarction, *Circulation*. 2007;116:0-0.

⁴Moussa ID, Klein LW, Shah B, et al. Consideration of a New Definition of Clinically Relevant Myocardial Infarction After Coronary Revascularization: An Expert Consensus Document From the Society for Cardiovascular

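### The troponin criterion for peri-procedural MI is timed from the PCI only, which contradicts the section's stated scope and, read literally, would under-count peri-CABG MI almost only in the HCR arm

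*Combined protocol and SAP*

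**What the plan says.** The definition is in the combined protocol and SAP, Definitions and Measurement of Endpoints, part B under Myocardial Infarction.

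- **Heading:** "Peri-PCI and Peri-CABG Myocardial Infarction".
- **Lead-in to the items:** "This definition applies to an event occurring ≤ 48 hours after any revascularization procedure as follows".
- **Markers:** CK-MB is preferred, "but cardiac troponin I or T may be used as described below".
- **Item a, CK-MB, normal baseline:** "The peak CK-MB measured within 48 hours of the procedure rises to" at least 10 times the upper limit of normal (ULN), or at least 5 times with new Q waves or persistent LBBB.
- **Item a, troponin:** this criterion is used only where CK-MB was not measured and the troponin baseline is normal. It is met if "a cardiac troponin (cTn) I or T level measured within 48 hours of the PCI rises to" at least 70 times ULN, or at least 35 times with the same ECG findings.
- **Missing baseline:** in stable CAD it is taken as normal, so item a applies.

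Treatment Interventions leaves the choice of marker open: "baseline cardiac biomarkers (CK-MB and/or Troponin T or I) and an electrocardiogram (ECG) must be performed in all patients prior to CABG and PCI". The same paragraph gives the purpose of the sampling as limiting ascertainment bias for peri-procedural MI.

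**The concern.** MI is one of the four components of the primary endpoint. Within one sentence, item a times one marker from any procedure and the other from PCI only. Troponin-only measurement is permitted, so the troponin criterion will be the operative one for some patients.

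Only the HCR arm has planned surgery. If the narrow wording were followed, a surgical MI documented by troponin alone would not count, while an MI with identical values after PCI would. The resulting error would run in one direction, towards HCR. It would also reach the interim analysis, which uses death, stroke or MI without revascularization and is the trial's one formal safety comparison. Missed MIs in the HCR arm would make harm from HCR harder to see there.

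**Working it through.** The definition rests on no planned figure, so there is none to reproduce. The check is a comparison of the texts.

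**1. Scope against item a**

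| Text | Procedures covered |
|---|---|
| Heading of part B | PCI and CABG |
| Lead-in sentence | any revascularization |
| Item a, CK-MB | the procedure (either) |
| Item a, troponin | the PCI |

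The first three agree. The fourth does not.

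**2. Does another rule cover a normal-baseline, troponin-only patient after CABG?**

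- The general permission to use troponin points to the items below it, so it returns to item a.
- Items b to d deal with elevated baselines, or with ACS patients lacking a baseline. They borrow their increments from item a and do not address a normal baseline.
- Part A (non-procedural MI) starts only after 48 hours.

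None does.

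**3. Who falls in the literal gap?** All three conditions are needed:

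- no CK-MB measured;
- baseline troponin normal, or assumed normal;
- no PCI within 48 hours of the CABG.

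Same-day hybrid procedures are allowed, and a troponin drawn after one can also lie within 48 hours of the PCI. However, the table under Treatment Assignments recommends CABG first with staged PCI. Treatment Interventions puts staged steps on separate calendar days and allows up to 90 days to complete them. The gap can therefore arise under the recommended sequence.

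**4. Does adjudication settle it?** The Clinical Events Committee section has the CEC adjudicate by the pre-specified definitions. Those contain both the broad scope and the narrow criterion, and the protocol does not say which prevails.

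**5. Scale, under assumptions.** From the documents: 2354 patients allocated 1:1, so 2354 / 2 = 1177 per arm; 5-year PCI MACCE of 25%; two-sided alpha of 0.05. Assumed: no true difference (25% in both arms), everyone followed for 5 years, and a fraction *m* of HCR patients whose only MACCE is an uncounted peri-CABG MI.

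- Observed HCR rate: p = 0.25 − m
- Apparent HR = ln(1 − p) / ln(0.75)
- Events: D = 1177 × (0.25 + p)
- P(significant, favouring HCR) = Φ(−1.96 + √(D/4) × |ln HR|)

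For m = 0.5%: p = 0.245, HR = 0.977, D = 1177 × 0.495 = 583, and Φ(−1.96 + 12.07 × 0.0234) = Φ(−1.68) = 4.7%.

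| m (assumed) | Uncounted (1177 × m) | Apparent HR | P(significant for HCR) |
|---|---|---|---|
| 0 | 0 | 1.00 | 2.5% |
| 0.25% | 3 | 0.99 | 3.4% |
| 0.5% | 6 | 0.98 | 4.7% |
| 1% | 12 | 0.95 | 8.2% |
| 2% | 24 | 0.91 | 21% |
| 3% | 35 | 0.86 | 41% |

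Nothing in the documents says where on this scale the trial would lie, or that *m* differs from zero.

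**The case against.** The strongest reply is that this is a drafting slip which a sensible committee would read past. The heading and lead-in name CABG or any revascularization. Items b and d accept troponin with no PCI restriction of their own, so the narrow reading would let troponin count after CABG when the baseline is elevated but not when it is normal. That is an unlikely intention. This point stands. A reader might infer that a troponin-only surgical MI can never qualify and that the primary result is therefore biased. The documents do not support that: they contain a contradiction, and its wider side includes CABG.

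The gap is also narrow, as step 3 shows, and some patients in it would still be events. Deaths count. So do separate unplanned procedures for CABG complications, and intervention for anterior ischemia before the planned staged PCI. Because the analysis is time to first event, a later MACCE also makes the patient an event, though at a later time. This stands too.

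A reader might also try to size the loss by multiplying a guessed MI rate by a guessed troponin-only share over the whole arm. With 2–5% and 20–80%, that gives 1177 × 0.02 × 0.20 = 4.7 to 1177 × 0.05 × 0.80 = 47.1 events. The documents support neither input, and the product ignores every restriction above. It should not be set against the designed difference of 25% versus 20%.

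The reply does not remove the contradiction. The CEC is bound to the written definitions, and the item that sets the troponin threshold is the one with the restriction.

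**Conclusion.** The wording of item a is wrong as it stands: its troponin criterion conflicts with the scope of its own section and with the CK-MB criterion beside it. The inconsistency is certain. Any bias is conditional on the CEC applying the literal wording to patients who meet all three conditions. If it did, peri-CABG MI would be under-counted almost only in the HCR arm, favouring HCR in primary MACCE and weakening the interim safety comparison.

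The size is unknown. The documents give no peri-CABG MI rate under these thresholds and no troponin-only share. The table in the working shows only how sensitive the test would be, and it assumes that the uncounted patients have no other MACCE.

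**What to change.** In item a, change the troponin window from 48 hours of *the PCI* to 48 hours of *the procedure*, matching the CK-MB criterion and the stated scope. Have the CEC apply that single wording to PCI and CABG in both arms. Do this before adjudication, since choosing a reading once MI counts by arm are known would be open to challenge.

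No separate rule on CK-MB precedence is needed, because item a already turns to troponin only when CK-MB is absent.

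The cost is that HCR may show slightly more early MI. No extra samples are needed, and alpha, power, the 530 events and the 2354 patients stay as planned.

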Only commercially available metallic drug-eluting stents may be used in this protocol. Because the use of DES on patients with left main disease or with three-vessel disease, both of which are off-label uses for DES, is considered investigational, this trial will be conducted under an Investigational Device Exemption (IDE). PCI should be performed using standard techniques at the discretion of the operator. In general PCI should be performed of lesions in vessels with visually estimated reference vessel diameter ≥ 2.25 mm with evidence of a) plaque rupture or thrombosis, or b) with an angiographic diameter stenosis $\geq 80\%$, or c) with evidence of ischemia on either non-invasive testing or by fractional flow reserve ≤ 0.80 or iFR ≤ 0.90 . Which of these criteria are met will be categorized. The specific adjunctive devices used (e.g. atherectomy, cutting/scoring balloons, or aspiration) and techniques (e.g. 1- vs. 2-stent and technique for treatment of bifurcation lesions) will be collected. Bioresorbable vascular scaffolds may not be used in this study.

Procedures may be staged at the discretion of the operator, but the intention to stage procedures must be specified within 24 hours after completion of the first procedure, should ideally be completed within 60 days of the first procedure, and in all cases must be completed within 90 of the first procedure after randomization.

For patients randomized to HCR, if off-pump CAB is performed first, prior to the staged PCI procedure a diagnostic angiogram of the LIMA-LAD graft must be performed, irrespective of the

Optimal Medical Management

All patients should be managed according to guideline-directed medical therapy (GDMT) by clinicians at each clinical site according to generally accepted societal recommendations. Details of GDMT are included in the MOP. Information will be collected about adherence to GDMT.

DEFINITIONS AND MEASUREMENT OF ENDPOINTS

Primary Endpoint

The primary endpoint for this trial is a composite of MACCE over 5 years following randomization.

All MACCE events will be adjudicated by an independent CEC. For the purpose of this trial **MACCE** is defined as a non-weighted composite score comprised of the following components:

- *All-cause mortality*
Death from any cause
- *Stroke*

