Note: Sudden unexpected cardiac death, involving cardiac arrest, often with symptoms suggestive of myocardial ischemia, and accompanied by new ST-segment elevation or new LBBB, and/or evidence of fresh thrombus by coronary angiography and/or autopsy, with death occurring before blood samples obtained, or at a time before the expected appearance of cardiac biomarkers in blood will be classified as a mortality due to peri-procedural MI.

○ *Unplanned Revascularization (adjudicated)*

(a) An unplanned revascularization procedure is defined as any PCI or CABG procedure performed that is an entirely new procedure due to ischemia not included in the pre-specified revascularization strategy, or (b) was included in the pre-specified revascularization strategy as a planned staged procedure, but was performed >90 days after the first revascularization procedure after randomization, or (c) that is a repeat intervention of a previously performed study-related revascularization. Determination as to whether the revascularization procedure involves an original target vessel and lesion or a new (non-target) vessel and lesion will be made by the CEC whenever possible.

Ischemia-driven Unplanned Revascularization

Ischemia-driven *unplanned* revascularization procedures will be assessed. All *unplanned* revascularization procedures will be reviewed and adjudicated by the CEC to determine if they are ischemia-driven. Revascularization will be considered ischemia-driven if the diameter stenosis of the revascularized coronary segment is $\geq 50\%$ or new thrombus and/or ulceration is present, and if any of the following criteria for ischemia are met: i) A positive functional study corresponding to the area served by the target lesion; or ii) Ischemic ECG changes at rest in a distribution consistent with the target vessel; or iii) Typical ischemic symptoms referable to the target lesion; or iv) IVUS of the target lesion with a minimal lumen area (MLA) of $\leq 4 \text{ mm}^2$ for non-left main lesions or $\leq 6 \text{ mm}^2$ for left main lesions; or v) FFR of the target lesion ≤ 0.80 or iFR of the target lesion < 0.90 . A target lesion revascularization for a diameter stenosis less than 50% might also be considered ischemia-driven by the CEC if there was a markedly positive functional study or ECG changes corresponding to the area served by the target lesion.

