Planned staged procedures which are declared within 24 hours of the first revascularization procedure or post randomization and are performed within 90 days of the first post-randomization revascularization procedure will not be considered an unplanned revascularization. Staged procedures performed >90 days after the first post-randomization revascularization procedure, even if originally pre-specified, will be considered an endpoint unplanned revascularization. Intervention on the LIMA, LIMA-LAD distal anastomosis or LAD triggered by routine LIMA angiography prior to a planned staged PCI will not be considered an unplanned revascularization. However, if anterior ischemia occurs after CABG necessitating LIMA angiography prior to the planned staged PCI with subsequent intervention on the LIMA, LIMA- LAD distal anastomosis or LAD, this event will be adjudicated as an unplanned revascularization.

Secondary Endpoints

The secondary endpoints for the trial (each measured at 30 days post procedure, 12, 24, 36, 48, and 60 months, unless otherwise specified) of the trial include:

Cardiovascular Events (adjudicated)

- *MACCE* (defined above) at 30 days post procedure, and 12, 24, 36, 48 months
- *Individual components of MACCE (adjudicated, as defined above):*
 - All-cause mortality
 - Stroke
 - Myocardial infarction
 - Unplanned revascularization
- Ischemia-driven revascularization (*adjudicated*)
- *Cardiovascular and Non-cardiovascular Mortality (adjudicated)*
Cardiovascular mortality, as adjudicated by the CEC, will be assessed. Cardiovascular death includes sudden cardiac death, death due to acute MI, heart failure or cardiogenic shock, stroke, other cardiovascular causes, or bleeding. Non- cardiovascular death is defined as any death with known cause not of cardiovascular causes. Any deaths in which the cause is unknown or undetermined will be considered cardiovascular.
- *Stent thrombosis (adjudicated)*
Stent thrombosis will be adjudicated according to the Academic Research Consortium scale.²⁵ Stent thrombosis will be considered to be present if criteria for definite or probable stent thrombosis are met. According to its timing, stent thrombosis will be further classified as acute (<24 hours), subacute (24 hours – 30 days), early (≤ 30 days), late (> 30 days – 1 year), or very late (> 1 year).
- *Symptomatic graft stenosis or occlusion (adjudicated)*

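### A planned stage done after day 90 can be scored ischemia-driven on the same evidence that first qualified the lesion for treatment

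*Combined protocol and SAP*

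**What the plan says.** Four parts of the protocol bear on this.

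- **Late stages become endpoint events.** The definition of unplanned revascularization has a limb (b) for planned stages done more than 90 days after the first post-randomization procedure. The text on planned stages repeats it: "Staged procedures performed >90 days after the first post-randomization revascularization procedure, even if originally pre-specified, will be considered an endpoint unplanned revascularization".
- **All unplanned procedures take the ischemia test.** Under Ischemia-driven Unplanned Revascularization, the CEC reviews every unplanned procedure. The anatomical condition is a diameter stenosis of at least 50%, or that "new thrombus and/or ulceration is present, and if any of the following criteria for ischemia are met". The criteria are: "i) A positive functional study corresponding to the area served by the target lesion"; resting ischemic ECG changes; "iii) Typical ischemic symptoms referable to the target lesion"; a small lumen area on IVUS; and "v) FFR of the target lesion" at or below 0.80, or iFR below 0.90. One is enough.
- **Lesions are selected on similar evidence.** Under Percutaneous Interventions (HCR Group & PCI-only Group), PCI is in general for lesions (a) "with evidence of a) plaque rupture or thrombosis", (b) "b) with an angiographic diameter stenosis" of at least 80%, or (c) "with evidence of ischemia on either non-invasive testing or by fractional flow reserve" ≤0.80 or iFR ≤0.90.
- **Staging differs by arm.** The opening of Treatment Interventions says HCR patients have planned staged procedures by design, while PCI patients may or may not. Both arms must finish within 90 days, with 60 recommended.

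Ischemia-driven revascularization is an adjudicated secondary endpoint. Analysis of Secondary End-points compares it by stratified log-rank test and by Poisson regression of the rate.

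**The concern.** An ischemia-driven label should mean that ischemia prompted the procedure. Here the ischemia criteria overlap with the grounds on which the lesion was put into the treatment plan, and nothing requires the evidence to be recent. A late stage can then carry the label because of scheduling alone.

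The opening of Treatment Interventions itself lists unplanned ischemia-driven procedures and procedures after 90 days as two separate kinds of endpoint event. The classification rule blurs that split for any lesion with its qualifying test on file. Because staging is commoner by design in the HCR arm, the mislabelling need not be balanced between arms.

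**Working it through.** The plan gives no figure to reproduce. The check is to write both rules as logic and apply them to lesions that have not changed.

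**Selection:** (a) plaque rupture or thrombosis; or (b) stenosis ≥80%; or (c) positive non-invasive test, FFR ≤0.80 or iFR ≤0.90.

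**Ischemia-driven:** [stenosis ≥50% or new thrombus/ulceration] AND [positive functional study, or resting ECG change, or typical symptoms, or small IVUS lumen area, or FFR ≤0.80, or iFR <0.90].

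The word new attaches only to thrombus/ulceration. The definitions of myocardial infarction do ask for new ST-T changes, new LBBB or new Q-waves, so the drafters asked for novelty where they wanted it.

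Unchanged lesion, planned stage done after day 90, only the evidence shown on file:

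| Lesion | Route | Anatomy met | Ischemia met | Ischemia-driven |
|---|---|---|---|---|
| 70%, FFR 0.75 | c | yes | yes | yes |
| 70%, positive non-invasive test | c | yes | yes | yes |
| 85%, typical symptoms | b | yes | yes | yes |
| 70%, thrombosis, typical symptoms | a | yes | yes | yes |
| 85%, no ischemia evidence | b | yes | no | no |
| 70%, thrombosis, no ischemia evidence | a | yes | no | no |
| 40%, thrombosis that is not new | a | no | no | no |
| 45%, positive non-invasive test | c | no | yes | no* |
| 70%, iFR exactly 0.90 | c | yes | no | no |

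*The CEC might still accept a stenosis below 50% if the functional study was markedly positive or ECG changes corresponded.

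So no selection route alone guarantees the label. Route (c) with at least 50% stenosis always earns it, except when it rests solely on an iFR of exactly 0.90. Routes (a) and (b) earn it only if symptoms or other ischemia evidence are also on file and stenosis is at least 50%.

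**Size.** The documents give neither the frequency of late stages nor the mix of selection routes. With 2354/2 = 1177 patients per arm, the excess of labelled late stages in HCR is

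1177 × (L_HCR − L_PCI) × q,

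where L is the proportion of patients with one late stage and q the share of late stages that meet the rule. All values below are assumptions.

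| Assumed L_PCI and q | L_HCR = 1% | L_HCR = 5% |
|---|---|---|
| L_PCI = 0, q = 1 | 1177 × 0.01 ≈ 12 | 1177 × 0.05 ≈ 59 |
| L_PCI = 0, q = 0.5 | ≈ 6 | ≈ 29 |
| L_PCI = 0, q = 0.25 | ≈ 3 | ≈ 15 |
| L_PCI = L_HCR/2, q = 0.5 | 1177 × 0.005 × 0.5 ≈ 3 | 1177 × 0.025 × 0.5 ≈ 15 |

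The range of about 3 to 59 shows how far the answer depends on the inputs. It is not an estimate.

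**The case against.** The strongest reply is that silence about dates is not an instruction to use old tests. The CEC reviews each case, the protocol elsewhere separates ischemia from lateness, and adjudication rules may exist in documents not available here. Running past 90 days also breaches a stated requirement, so it should be uncommon. And for an untreated lesion with FFR 0.75, calling the revascularization ischemia-driven is not plainly false.

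Part of this stands. The CEC could adopt a sensible convention, and late stages may be few. But the definition sends late planned stages through the test without exception, and its literal terms are met by the file that justified the plan. That is a rule which mislabels late scheduling, not just a gap.

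A reader might infer more than the text supports:

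- *That every late stage would be labelled.* Selection routes (a) and (b) need no ischemia evidence. Also, the selection text is general guidance for PCI lesions and does not govern a late LIMA-LAD stage after PCI-first HCR.
- *That every endpoint threshold is as loose as selection or looser.* For iFR the endpoint (<0.90) is slightly stricter than selection (≤0.90).
- *That only HCR is exposed.* Staged PCI is an explicit option under the same 90-day limit. Same-day HCR, and LIMA-LAD alone after earlier PCI, are allowed and involve no later stage.
- *That a stated inflation of the HCR rate or of the type I error follows.* Any such figure rests on inputs that the documents do not contain.

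**Conclusion.** The point holds in a limited form. A planned stage done more than 90 days after the first procedure can be scored ischemia-driven on pre-existing evidence, provided the lesion has at least 50% stenosis and a positive functional study, FFR ≤0.80, iFR <0.90 or typical symptoms on file. It does not hold for lesions selected only for ≥80% stenosis or plaque rupture/thrombosis without ischemia evidence.

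The consequence is confined to the ischemia-driven secondary endpoint and its log-rank and Poisson comparisons. The primary MACCE count does not move, because a late stage already counts there as unplanned revascularization. The misclassification may fall more on HCR, given how the two arms are staged, but the documents do not establish its size. The conclusion rests on the protocol definition as written and assumes that no separate CEC rule overrides it. The change is worth making because it is cheap and best settled before adjudication.

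**What to change.** Add to the Ischemia-driven Unplanned Revascularization definition, in substance: *for a lesion in the pre-specified plan that has not yet been treated, the ischemia evidence must have been obtained after the last completed study procedure and must be the reason for the revascularization. Persistent or new symptoms, ECG change, or a clinically prompted functional or FFR/iFR study qualify. The baseline test that qualified the lesion, or a routine re-measurement at the scheduled stage, does not.* Persistent symptoms should be named: a requirement for new or worsening symptoms would wrongly exclude a patient treated for continuing angina.

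Keep late planned stages within unplanned revascularization, so that MACCE is untouched. Add a CEC form field that flags them, and report ischemia-driven revascularization with and without late planned stages, by arm.

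The cost is a short addition to the definition, one form field and one extra tabulation, with slightly fewer ischemia-driven events. The protocol already has staging intent and the PCI selection criteria recorded, so little new data are needed beyond the date of the qualifying evidence and the reason for the procedure. No treatment rule changes.
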